**Table 16.2-2 Analysis Time Windows for Efficacy Analysis - Weekly Questions**

Analysis Week	Begins a	Ends a
Week -2	Visit 2 day	Visit 2 day + 7
Week -1 (Baseline)	Visit 2 day + 8	Day 1
Week 1	Day 2	Day 8
Week 2	Day 9	Day 15
Week 3	Day 16	Day 22
Week 4	Day 23	last dose date +1
Postintervention	day of last dose date + 8	day of end of study visit

a Begin and end of each week from Week 1 onwards are relative to the date of the first dose of double-blind study intervention. Day 1 = the date of the first dose of double-blind study intervention. There is no Day 0 or Week 0. End of Week 1 to Week 4 will be day of last dose + 1 or corresponding end day in table whichever comes earlier.

Global severity of child's constipation will be collected starting from Preintervention Visit (Visit 2) and global change in child's constipation will be collected starting one week after Randomization visit.

## 16.3 DERIVED VARIABLES

### 16.3.1 Missed eDiary Assessments

No imputation or derivation will be performed for missed eDiary assessments unless otherwise specified.

### 16.3.2 Incomplete eDiary Assessments

Missing responses in incomplete eDiary assessments will not be imputed for most of the parameters, with the exception of rescue medication (RM) use and BM frequency.

If the answer to the RM use question is missing in eDiary, no RM usage will be considered during that diary period in eDiary.

If the answer to the question related to BM frequency is missing in any daily eDiary, BM frequency will be considered as zero for that diary period in the eDiary.

### 16.3.3 Incomplete Clinic Diary on Randomization Visit

Missing responses in an incomplete clinic diary on randomization day will be handled in a similar way as mentioned for incomplete daily eDiary assessments.

### 16.3.4 Stool frequency

#### *Spontaneous Bowel Movement (SBM)*

A SBM is a BM that occurs in the absence of laxative, suppository, or enema use on the calendar day of the BM or the calendar day before the BM.

#### *Stool Frequency Rates*

The components for calculating a participant's stool frequency rates (SBM weekly rates) for a given period are as follows:

- The number of BMs that occurred during that specific period
- The number of those BMs that were SBMs
- The number of days during that specific period:
- Randomization day will be considered as a half day for the double-blind Intervention Period and Preintervention Period.

#### *Duration of an Analysis Week*

With respect to a participant's scheduled analysis weeks, the term duration is used. In regard to the duration of a week, it is expected that 1 or more of a participant's "weeks" may not be exactly 7 days in duration (eg, a participant may withdraw or discontinue early from the trial or may have missing diary day). Deviations from the 7 days norm are structural in nature; and, as such, the calculations of the weekly rates of SBMs will incorporate the actual days contributed within the time period (week or specific phase).

### ***Weekly Stool Frequency Rate Calculations***

The weekly frequency rate for SBMs will be based on the total number of SBMs reported by a caregiver as being directly observed by the caregiver based on the diary entries during that time period, adjusting for differences in the length of the time period. Weekly stool frequency rates for each specific period will be calculated as follows:

$$\text{Weekly Frequency Rate (Specific Period)} = \frac{\text{Total number of SBMs reported by a caregiver as being directly observed during the specific time period}}{\text{Number of days during the specific analysis period}} \times 7$$

The weekly frequency rate for SBMs will also be derived based on the total number of SBMs occurring based on the diary entries during that time period (including SBMs not directly observed by the caregiver), adjusting for differences in the length of the time period.

Weekly Frequency Rate (Specific Period) including SBMs not directly observed by caregiver =

$$\frac{\text{Total number of events (SBMs) during the specific period}}{\text{Number of days during the specific period}} \times 7$$

#### **16.3.5 Stool Consistency**

The caregiver will be asked to rate the child's observed stool consistency for each BM the caregiver was present for using the Bristol Stool Form Scale (BSFS), a 7-point ordinal scale:

"Choose the option that is most like the Xth (eg, 1st, 2nd, 3rd, ...) bowel movement you were with the child for"

- Type 1: Separate hard lumps, like nuts (hard to pass)
- Type 2: Sausage-shaped, but lumpy
- Type 3: Like a sausage but with cracks on its surface
- Type 4: Like a sausage or snake, smooth and soft
- Type 5: Soft blobs with clear cut edges (easy to pass)
- Type 6: Fluffy pieces with ragged edges, a mushy stool
- Type 7: Watery, no solid pieces. Entirely liquid
- 99 - I don't know

A participant's stool consistency score for the Study Intervention Period will be the average of the non-missing BSFS scores for the caregiver-observed SBMs during that specific period.

### 16.3.6 Straining

If the caregiver was present for the BM, the caregiver will be asked to rate the amount of straining observed when the child passed the BM using the following two 3-point rating scales. The caregiver will be asked to assess the degree of straining for every BM for which he/she was present by responding to the following two questions in the daily eDiary:

The participant's daily straining score for each caregiver-observed BM will be derived based on the average of non-missing responses of the two straining questions. The participant's straining score will be the average of the non-missing daily average straining scores for the caregiver-observed SBMs during the specific period.

### 16.3.7 Fecal Incontinence (For Participants Who Have Acquired Toileting Skills Only)

Caregivers of children who have acquired toileting skills for BMs will be asked about their child's fecal incontinence episodes. Toileting skills will be assessed as part of the first daily diary and responses will be carried through to the completion of the study.

Caregivers will be asked the following:

Caregivers who choose the first response option for toilet training status [REDACTED] at the start of the study will be presented with the following question assessing daily fecal incontinence throughout the course of the study:

If the caregiver replies "Yes" to the question above, they will be presented with the following question:

Caregivers who choose the second option for toilet training status [REDACTED] at the start of the study will be presented with the following question assessing daily fecal incontinence throughout the course of the study:

Any "yes" response for the question related to the [REDACTED] will be counted as presence of fecal incontinence in the corresponding day.

### 16.3.8 Global Items

[figure not shown]
The global items consist of two items, one assessing global change in the child's symptoms and one assessing the global severity of the child's symptoms. Both global items will be completed weekly on the eDiary by the caregiver. The global severity item will be completed beginning at the Preintervention Period through the End-of-Study and the global change item will be completed beginning at one week after Randomization through the End-of-Study.

#### Global Change Item

The global change item assesses the change in the child's constipation (1 item) as follows:

#### Global Severity Item

The global severity item assesses the severity of the child's constipation (1 item) as follows:

**16.4 REPEATED OR UNSCHEDULED ASSESSMENTS OF SAFETY PARAMETERS**

If a participant has repeated assessments before the start of the first study intervention, the results from the final non-missing assessment made prior to the start of the study intervention will be used as baseline as appropriate unless specified. If end-of-study assessments are repeated or if unscheduled visits occur, the last non-missing postbaseline assessment will be used as the end-of-study assessment for generating summary statistics. However, all postbaseline assessments will be used for PCS value determinations, and all assessments will be presented in the data listings.

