8.2.4. Clinical Safety Laboratory Assessments

- See Section 10.2 for the list of clinical laboratory tests to be performed and the SoA (Section 1.3) for the timing and frequency.
- At Screening (Visit 1), the investigator will assess the clinical significance of any values outside the reference ranges provided by the laboratory, and participants with abnormalities judged to be clinically significant will be excluded from the study.
- The investigator must review the laboratory report, document this review, and record any clinically relevant changes occurring during the study in the AE section of the eCRF. The

- laboratory reports must be filed with the source documents. Clinically significant abnormal laboratory findings are those which are not associated with the underlying disease, unless judged by the investigator to be more severe than expected for the participant's condition.
- All laboratory tests with values considered clinically significant during participation in the study or within 30 days after the last dose of study intervention should be repeated until the values return to normal or baseline or are no longer considered clinically significant by the investigator or medical safety physician.
 - If such values do not return to normal/baseline within a period of time judged reasonable by the investigator, the etiology should be identified, and the sponsor notified.
 - O All protocol-required laboratory assessments, as defined in Section 10.2, must be conducted in accordance with the SoA and the laboratory manual.
 - o If laboratory values from non-protocol specified laboratory assessments performed at the institution's local laboratory require a change in participant management or are considered clinically significant by the investigator (eg, SAE or AE or dose modification), then the results must be recorded in the eCRF.

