Shift tables from baseline to the end of double-blind Intervention Period for clinical laboratory parameters listed above will be presented by study intervention group within the corresponding cohort for the following categories: low, normal, and high, which are provided by lab vendor.

The PCS summaries for laboratory parameters and shift table from baseline to the end of double-blind Intervention Period will also be provided combining participants from the similar linaclotide dose cohorts (if any) and combining participants from all cohorts in the placebo group.

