**Table 16.1–1 Visit Time Windows**

Derived Visit	Scheduled Visit Daya	Window
Baseline	Day 1	Days ≤ 1
Week 2 Visit	Day 15	Days [2, 21]
Week 4 Visit	Day 29	Days [Day 22, max (last dose day+1, Visit 5 date)]
Postintervention Visit	Day 36	Days ≥ max (last dose day+1, Visit 5 date)+1
End of Double-Blind Intervention Period b	Final or Termination Visit during the double-blind Intervention Period	

a Relative to the date of the first dose of double-blind study intervention. Day 1 = the date of the first dose of double-blind study intervention. There is no Day 0 or Week 0.

b Presented in analysis tables for safety parameters, including but not limited to electrocardiograms, clinical laboratory values, and vital signs.

If the assessment date (if the assessment date is unavailable, use visit date instead) is on or after the date of the first dose of study intervention, the study day is calculated by assessment date – date of the first dose of study intervention + 1. If the assessment date is before the date of the first dose of study intervention, the study day is calculated by assessment date – date of the first dose of study intervention. Therefore, a negative day indicates a day before the start of the study intervention.

If a participant has 2 or more visits within the same window, the last visit with a non-missing value will be used for analysis.

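### Laboratory means and the laboratory and ECG shift tables keep only the last value, so an on-treatment abnormality that recovers can be missing from them, and PCS counts only partly fill the gap

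*SAP*

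**What the plan says.** **Retesting.** Protocol 8.2.4 covers "All laboratory tests with values considered clinically significant during participation in the study or within 30 days after the last dose of study intervention". Such tests "should be repeated until the values return to normal or baseline or are no longer considered clinically significant". The rule is confined to laboratory tests and to results judged clinically significant. The same section has clinically relevant changes entered as adverse events.

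**Choice of value.** Under Table 16.1–1 the SAP states: "If a participant has 2 or more visits within the same window, the last visit with a non-missing value will be used for analysis". SAP 16.4 adds that, with repeats or unscheduled visits, "the last non-missing postbaseline assessment will be used as the end-of-study assessment for generating summary statistics". It then makes an exception: "all postbaseline assessments will be used for PCS value determinations, and all assessments will be presented in the data listings".

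**Windows.** Week 2 covers Days 2 to 21. Week 4 runs from Day 22 to the later of the day after last dose and the Visit 5 date. The Postintervention window is "Days ≥ max (last dose day+1, Visit 5 date)+1".

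**Tables.** SAP 11.2 plans "Shift tables from baseline to the end of double-blind Intervention Period for clinical laboratory parameters listed above", using low, normal and high categories. SAP 11.4 plans a similar end-of-period shift for the investigator's ECG interpretation. It also plans a display of participants with clinically significant postbaseline ECGs. SAP 11.3 plans no shift table for vital signs.

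**Schedule.** Laboratory tests and ECG are scheduled at Screening and Visit 5 only. For a completer, Visit 5 is also the day of the last dose, Day 29 (+2).

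**The concern.** Retesting is triggered by an abnormal result and ends once that result has resolved. If the analysis then keeps the last value, it tends to select the recovered one, and it does so in the children who had an abnormality. Because no laboratory draw is scheduled between Day 1 and Visit 5, an electrolyte disturbance during diarrhea in the first weeks can be seen only in an unscheduled sample. Those are the samples that the last-value rule discards.

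The adverse events of special interest (AESIs) in this trial are diarrhea-related volume depletion, electrolyte disturbance and ECG abnormality. The analysis is descriptive and the arms are very small, so one child who is recorded as normal throughout visibly changes the table.

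**Working it through.** The plan gives no figure to reproduce here. The check applies the Table 16.1–1 windows to dated samples and then looks at what the PCS tables would recover. The sample dates are illustrative.

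**1. Which value is analysed**

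For a completer with Visit 5 and last dose on Day 29, the Week 4 window ends on max(29 + 1, 29) = Day 30.

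| Sequence | Under Table 16.1–1 | Under SAP 16.4 read literally |
|---|---|---|
| Abnormal Day 10, normal repeat Day 14, normal Visit 5 Day 29 | Week 2 uses Day 14; the shift uses Day 29; abnormality not shown | Not shown |
| Abnormal Visit 5 Day 29, normal repeat Day 30 | Both in Week 4; Day 30 used; not shown | Not shown |
| Abnormal Visit 5 Day 29, normal repeat Day 31 or later | Repeat is Postintervention; the Visit 5 value stays; **shown** | Repeat replaces Visit 5; not shown |

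In the first row the abnormality is lost under either reading, for two separate reasons. The repeat displaces it in the Week 2 mean, and the shift table looks only at the end of the period. In the third row the two rules give opposite answers, and the SAP does not say which governs.

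For an early discontinuer with last dose on Day 10 and the end-of-treatment visit on Day 14, the Postintervention window starts on max(10 + 1, 14) + 1 = Day 15. A repeat on Day 17 then falls both in Week 2 (Days 2 to 21) and in Postintervention, so the table does not settle which value is used.

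**2. What the PCS tables recover**

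Table 11.2-1 flags sodium and potassium below 0.9 × LLN (lower limit of normal) or above 1.1 × ULN (upper limit of normal). The laboratory's limits are not in the documents. With assumed ranges:

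- Sodium LLN 133 to 136 mmol/L: 0.9 × 133 = 119.7 and 0.9 × 136 = 122.4.
- Potassium LLN 3.3 to 3.5 mmol/L: 0.9 × 3.3 = 2.97 and 0.9 × 3.5 = 3.15.

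A sodium of 129 on an unscheduled draw would be low but not PCS anywhere in that range. If a later value replaces it, no laboratory summary table shows it.

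Magnesium and phosphate are on the SAP 11.2 list of analysed parameters, but Table 11.2-1 has no limit for either. For these two there is no PCS count at all.

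The SAP 11.2 display of all postbaseline values is restricted to participants with a PCS value. Other children's values appear only in the general listings.

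**3. Size**

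- Active arm of Cohorts 1 to 3: 8 × 3/4 = 6 children. One masked shift changes 1/6 = 16.7% to 0/6.
- Pooled with the final cohort at the same dose: 6 + 5 = 11 children. One masked shift changes 1/11 = 9.1% to 0/11.

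These figures give the effect of one case. The documents do not allow an estimate of how often it would occur.

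**The case against.** The strongest reply is that a clinically significant on-treatment abnormality is not lost. Protocol 8.2.4 sends clinically relevant changes to the adverse event page. SAP 11.1 then tabulates treatment-emergent events by severity and causality and displays AESIs separately. PCS determinations use all postbaseline values, and listings show everything. This stands. A reader might infer that such an event vanishes from every summary, and the documents do not support that. What is missing is a summary of the laboratory values themselves: adverse event tables give a coded term and a severity, and depend on the investigator's judgement of relevance.

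A second reply is that Visit 5 is both the only scheduled draw and the last-dose day, so repeats of an abnormal Visit 5 result will often come more than one day later. Under Table 16.1–1 those repeats are Postintervention and the abnormal value stays. This also stands. It would be wrong to say that recovered repeats generally overwrite Visit 5, but the protection depends on Table 16.1–1 prevailing over SAP 16.4, which the SAP does not state.

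A third reply is that when a normal scheduled Visit 5 follows an earlier abnormality, the shift table merely reports the end of the period and no repeat has displaced anything there. That is correct, and it is why choosing the scheduled value would not be enough without a worst-value shift.

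Finally, one might extend the point to ECGs and vital signs. The retest-until-resolved rule covers laboratory tests only. For ECG, the existing display of clinically significant findings limits the issue to the shift table. Vital signs have no shift table, and no such retesting rule applies to them.

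**Conclusion.** The point holds as a limited gap in the laboratory summaries and an unresolved conflict between two SAP rules. An unscheduled on-treatment laboratory abnormality that recovers by an in-window repeat or by Visit 5 does not appear in the end-of-period shift table. An in-window repeat or later draw also removes it from the by-visit means. PCS counts cover this only for parameters that have PCS limits and for values beyond them. Sodium between LLN and about 120 to 122 mmol/L (assumed LLN 133 to 136), and every magnesium and phosphate value, are left without a laboratory summary of the worst value. Separately, SAP 16.4 read literally would let a post-treatment repeat replace an abnormal Visit 5 result, contrary to Table 16.1–1.

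The documents do not support the stronger reading that the plan hides clinically significant events, because adverse event and AESI displays, PCS tables and listings remain. Each masked child is worth 16.7 percentage points in an active arm of six. The window results follow from the SAP and the illustrative dates; the numerical PCS cut-offs rest on the assumed laboratory limits. This is a worthwhile, inexpensive improvement, and it does not undermine the safety analysis as a whole.

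**What to change.** - **SAP 11.2 and 11.4:** add shift tables from baseline to the worst on-treatment value, with lowest and highest shown separately for laboratory parameters and the worst investigator interpretation for ECG. Use all scheduled, unscheduled and repeat values from first dose to max(last dose day + 1, Visit 5 date).
- **SAP 16.1 and 16.4:** state that Table 16.1–1 governs the end of the double-blind period. Use the scheduled-visit value (first valid result) for by-visit and end-of-period statistics. Remove or define the end-of-study assessment in 16.4, and settle the Week 2 and Postintervention overlap for early discontinuers.

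The cost is SAP wording and one extra set of tables. No new data are needed.

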**16.5 MISSING DATE OF THE LAST DOSE OF STUDY INTERVENTION**

When the date of the last dose of study intervention is missing for a participant in the Safety Population, all efforts should be made to obtain the date from the Investigator. If after all efforts are made it is still missing, the Visit 5 date (if available) will be set as last dose date. In absence of the Visit 5 date, the double-blind disposition status date will be set as last dose date.

**16.6 MISSING SEVERITY ASSESSMENT FOR ADVERSE EVENTS**

If severity is missing for an AE that started before the date of the first dose of study intervention, an intensity of mild will be assigned. If severity is missing for an AE that started on or after the date of the first dose of study intervention, an intensity of severe will be assigned. The imputed values for severity assessment will be used for the incidence summary; the values will be shown as missing in the data listings.

**16.7 MISSING CAUSAL RELATIONSHIP TO STUDY DRUG FOR ADVERSE EVENTS**

If the causal relationship to the study intervention is missing for an AE that started on or after the date of the first dose of study intervention, a causality of yes will be assigned. The imputed values for causal relationship to study intervention will be used for the incidence summary; the values will be shown as missing in the data listings.

**16.8 MISSING DATE INFORMATION FOR ADVERSE EVENTS**

The following imputation rules only apply to cases in which the start date for AEs is incomplete (ie, partly missing).

**Missing month and day**

- If the year of the incomplete start date is the same as the year of the first dose of study intervention, the month and day of the first dose of study intervention will be assigned to the missing fields
- If the year of the incomplete start date is before the year of the first dose of study intervention, *December 31* will be assigned to the missing fields
- If the year of the incomplete start date is after the year of the first dose of study intervention, *January 1* will be assigned to the missing fields

**Missing month only**

- If only the month is missing, the day will be treated as missing and both the month and the day will be replaced according to the above procedure

**Missing day only**

- If the month and year of the incomplete start date are the same as the month and year of the first dose of study intervention, the day of the first dose of study intervention will be assigned to the missing day
- If either the year of the incomplete start date is before the year of the date of the first dose of study intervention or if both years are the same but the month of the incomplete start date is before the month of the date of the first dose of study intervention, the last day of the month will be assigned to the missing day
- If either the year of the incomplete start date is after the year of the date of the first dose of study intervention or if both years are the same but the month of the incomplete start date is after the month of the date of the first dose of study intervention, the first day of the month will be assigned to the missing day

If the stop date is complete and the imputed start date as above is after the stop date, the start date will be imputed by the stop date.

If the start date is completely missing and the stop date is complete, the following algorithm will be used to impute the start date:

- If the stop date is after the date of the first dose of study intervention, the date of the first dose of study intervention will be assigned to the missing start date
- If the stop date is before the date of the first dose of study intervention, the stop date will be assigned to the missing start date

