### **11.1 ADVERSE EVENTS**

Adverse events will be coded by system organ class and preferred term using the *Medical Dictionary for Regulatory Activities*, version 23.0 or newer.

An AE will be considered a treatment-emergent adverse event (TEAE) if

- The AE began on or after the date of the first dose of study intervention; or
- The AE was present before the date of the first dose of study intervention, but increased in severity or became serious on or after the date of the first dose of study intervention

An AE that occurs more than 1 day after the last dose of study intervention will not be counted as a TEAE.

An AE will be considered a treatment-emergent serious adverse event (TESAE) if it is a TEAE that additionally meets any serious adverse event (SAE) criterion.

The number and percentage of participants reporting TEAEs in each study intervention group will be tabulated by descending percentage in any group, by system organ class and preferred term, and further categorized by severity and causal relationship to the study intervention. If more than 1 AE is coded to the same preferred term for the same participant, the participant will be counted only once for that preferred term using the greatest severity and strictest causality for the summarization by severity and causal relationship.

For the all screened participants, separate tabular displays will be presented for participants who died, participants with SAEs, participants with AEs leading to premature discontinuation, and participants with AEs of special interest. AEs during the Postintervention Period will also be included in the listings. Listing of all AEs will also be presented.

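### When severity, causality or the whole start date is missing, the SAP's imputation rules treat some treatment-emergent adverse events less conservatively than comparable ones

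*SAP*

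**What the plan says.** SAP 11.1 defines a treatment-emergent AE (TEAE) by two limbs. The first is onset: "The AE began on or after the date of the first dose of study intervention". The second covers earlier events: "The AE was present before the date of the first dose of study intervention, but increased in severity or became serious on or after" that date. An event more than one day after the last dose is excluded. Protocol 9.4.2.1 gives the same definition. TEAEs are then tabulated by severity and by causal relationship.

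Three data-handling sections feed those tables:

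- **SAP 16.6 (missing severity).** For an AE that "started before the date of the first dose of study intervention, an intensity of mild will be assigned". For an AE with onset on or after that date the grade is severe.
- **SAP 16.7 (missing causality).** The rule has one condition: "If the causal relationship to the study intervention is missing for an AE that started on or after the date of the first dose", causality is set to yes. Earlier onset has no rule.
- **SAP 16.8 (missing start date).** Partly missing dates have a full set of rules. A completely missing start date has one rule: "If the start date is completely missing and the stop date is complete, the following algorithm will be used to impute the start date". It has two branches. "If the stop date is after the date of the first dose of study intervention", the start becomes the first-dose date. In the other, an earlier stop is used as the onset: "If the stop date is before the date of the first dose of study intervention, the stop date will be assigned to the missing start".

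**The concern.** The TEAE definition has two limbs, but 16.6 and 16.7 recognise only the first. A child whose AE began before dosing and became serious on study intervention has a TEAE under 11.1. If its severity was never recorded, the SAP assigns the lowest of the three grades in Protocol Appendix 3. The same gap in a TEAE with onset after dosing is filled with the highest grade. Causality shows the same split between a yes and no rule at all.

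In 16.8 the asymmetry concerns unresolved events. An undated AE that resolved after the first dose is placed on the first-dose date and counted. An otherwise identical AE that has not resolved gets no date.

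Worst-case imputation exists to avoid undercounting harm, and these are the cases it misses. Pre-dose onset is plausible here. AEs are collected from consent (Protocol 8.3.2), and Screening takes place 4 to 7 weeks before randomization (Protocol 10.8.1). That interval includes dis-impaction for children found impacted at Screening and access to rescue laxatives from Visit 2.

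**Working it through.** The documents give no figure to reproduce. The check applies the rules literally to each possible record.

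**Step 1. Start-date patterns under SAP 16.8, for an AE that does not worsen.**

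| Start date | Stop date | Start assigned | TEAE under 11.1 |
|---|---|---|---|
| Day missing, same month as first dose | none | first-dose date | yes |
| Month and day missing, same year as first dose | none | first-dose date | yes |
| Day missing, earlier month | none | last day of that month | no |
| Completely missing | after first dose | first-dose date | yes |
| Completely missing | before first dose | stop date | no |
| Completely missing | equal to first-dose date | no rule | cannot be evaluated |
| Completely missing | partial | no rule | cannot be evaluated |
| Completely missing | none (ongoing) | no rule | cannot be evaluated |

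The first five rows fit the definition. The last three have no rule. Without a start date the onset limb cannot be met. The second limb needs the event to be known as pre-dose; the visit of record could show that, but the SAP does not say to use it. By contrast, SAP 16.9 imputes incomplete stop dates for medications, and 16.8 has no such rule for AEs.

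**Step 2. Severity and causality for TEAEs under 16.6 and 16.7.**

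| TEAE | Severity if missing | Causality if missing | If recorded |
|---|---|---|---|
| Onset on or after first dose | severe | yes | unchanged |
| Pre-dose onset, became serious on or after first dose | mild | no rule | unchanged |

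The second row assumes that the pre-dose start date stays on the record. Protocol 8.3.4 suggests so, because updates go into the originally completed eCRF.

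**Step 3. Weight of one child.** Inputs are the cohort sizes and ratios in SAP 4.0, with all four cohorts full.

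- Cohorts 1 to 3: 8 × 3/4 = 6 linaclotide, 8 × 1/4 = 2 placebo.
- Final cohort: 6 × 5/6 = 5 linaclotide, 6 × 1/6 = 1 placebo.
- Pooled top dose, if the final cohort repeats the dose of one earlier cohort: 6 + 5 = 11.
- Pooled placebo: 2 + 2 + 2 + 1 = 7.

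| Denominator | One child |
|---|---|
| Linaclotide, Cohorts 1 to 3 | 1/6 = 16.7% |
| Linaclotide, final cohort | 1/5 = 20.0% |
| Pooled top dose | 1/11 = 9.1% |
| Placebo, Cohorts 1 to 3 | 1/2 = 50% |
| Placebo, final cohort | 1/1 = 100% |
| Pooled placebo | 1/7 = 14.3% |

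These are the most that one record can move a cell. An uncounted AE changes a child's entry in a row only if the child has no other qualifying event in that row. A grade of mild in place of severe moves severity cells, not overall incidence.

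**The case against.** The case on the other side is substantial, and most of it limits the size of the problem.

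- **A reader might infer that every pre-dose AE that becomes serious is set to mild and unrelated.** The SAP does not say this. Sections 16.6 and 16.7 act only on missing fields.
- **A reader might infer that the SAP removes undated ongoing AEs from the TEAE tables.** No sentence does so. Their status is unspecified, and exclusion is what literal programming would produce. Likewise, the SAP does not say how a pre-dose-onset TEAE with missing causality is tabulated.
- **The worsening case is nearly empty.** Showing that severity increased normally requires a recorded severity, and then 16.6 does not apply. The live case is an event that became serious with no grade. Protocol Appendix 3 keeps seriousness and severity separate, so this can occur.
- **Missing data should be rare.** Appendix 3 asks for a causality assessment of every event before the first transmission of a serious AE. AEs are queried at each visit, which brackets onset, and the data undergo edit checks and source verification.
- **Nothing is hidden.** SAP 11.1 lists all AEs. It displays deaths, serious AEs, AEs of special interest and AEs leading to discontinuation separately, and imputed values appear as missing in the listings.
- **The gap is not specific to linaclotide.** In a placebo arm, an uncounted event would make linaclotide look relatively worse.

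All of this stands. What it does not answer is that the SAP fills the same missing field in opposite ways for two TEAEs, and gives an unresolved undated event less protection than a resolved one.

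**Conclusion.** The point holds and is minor. For missing severity and causality, the start-date condition in 16.6 and 16.7 does not fit the second limb of the TEAE definition in 11.1. For a completely missing start date, 16.8 has a gap: ongoing AEs, partial stop dates and a stop on the first-dose date are not covered. The remaining branches of 16.8 agree with the definition.

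Within an arm, the effect is toward fewer or milder TEAEs than the SAP's own treatment of comparable events would give. Between arms it can go either way. Few if any records are expected, and the listings keep every event visible. The conclusion rests on literal application of the text and on the pre-dose start date being retained when an AE worsens or becomes serious. The reason to act is that in arms this small, one case settled by an ad hoc programming choice would be visible in the tables.

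**What to change.** - **SAP 16.6 and 16.7:** replace the start-date condition by TEAE status. For every TEAE under either limb of 11.1, missing severity becomes severe and missing causality becomes yes. Mild is kept for non-TEAEs only.
- **SAP 16.8:** add that a completely missing start date not covered by the existing rules is set to the first-dose date, unless the AE was first recorded before the first dose or its partial stop date is clearly before the first dose. In those cases it is treated as pre-dose. Without this exception, AEs already recorded at Visit 1 or 2 would become TEAEs.

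The cost is a few lines of SAP text and a small programming change before unblinding. A TEAE incidence or severity count may become slightly less favourable. An undated event first reported at Visit 6 would be counted even if it began outside the limit of last dose plus one day. The existing branch for undated resolved events already leans the same way.
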